8.1.4.2 Adverse Events

Adverse events will be coded using the most current version of the Medical Dictionary for Regulatory Activities (MedDRA). Adverse events will be summarized by primary MedDRA system organ class (SOC) and preferred term (PT). Subjects reporting more than one adverse event for a given MedDRA PT will be counted only once for that term. Subjects reporting more than one adverse event within an SOC will be counted only once for the SOC total. Subjects reporting more than one adverse event will be counted only once in the overall adverse event total.

Each adverse event will be categorized by severity (mild, moderate, severe) and by relationship to study treatment (reasonable possibility, or no reasonable possibility). Detailed search criteria for adverse events of special interest (AESIs) will be defined in a SAP prior to database lock.

A treatment-emergent adverse event (TEAE) is defined as:

- For OMT group: any adverse event that begins or worsens in severity the day after randomization and within 30 days following the last visit.
- For the LCIG group: any adverse event that begins or worsens in severity from the day of the initial device placement (NJ or PEG-J) through Week 26 Visit for those subjects continuing to LCIG commercial treatment, or through 30 days after final device removal for those subjects not continuing LCIG commercial treatment.

A summary of the number and percentage of subjects will be prepared for the following:

- TEAEs
- TE Serious AEs (including deaths)
- TEAEs leading to premature discontinuation of treatment
- TEAEs by maximum relationship to study drug
- TEAEs by maximum severity
- Treatment-emergent AESIs

Serious adverse events with onset during the Screening Period for all subjects screened, adverse events and serious adverse events with onset after day of randomization and before day of initial device placement for the LCIG group, as well as adverse events during the transition period for LCIG subjects continuing LCIG commercial treatment will also be summarized.

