For subjects randomized to the LCIG group, the date and time of the earliest LCIG tube placement (NJ or PEG-J) recorded on the Device Information eCRF will be considered

the treatment start reference date (REFDT1) and time (DMREFTM). The date of the last LCIG tube removal, or the date of the last LCIG infusion if there is no device removal in the 26-week randomized period will be considered as end of the LCIG 26-week randomized treatment period and the following day will be the post-treatment start reference date (REFEDT1). For LCIG subjects who enter the Extension Period, treatment start reference date in extension period (REFDT2) equals REFEDT1. The date of the last LCIG tube removal or the date the last LCIG infusion if there is no device removal, will be the post-treatment reference date (REFEDT2) of Extension Period.

For subjects in the OMT group, the date after randomization will be considered the treatment start reference date (REFDT1). The date of the final visit during 26-week randomized period will be considered the end of the OMT treatment period and the following day will be the post-treatment start reference date (REFEDT1). For OMT subjects who enter the Extension Period, the date of earliest LCIG tube placement (NJ or PEG-J) recorded on the Device Information eCRF will be considered the treatment start reference date (REFDT2) in Extension period. The date of the last LCIG tube removal, or the date the last LCIG infusion if there is no device removal, will be considered the end of the Extension Period and the following day will be the post-treatment start reference date (REFEDT2).

Study Days during 26-week randomized treatment period will be calculated based on the treatment start reference date (REFDT1). For time points before REFDT1, the Study Day = time point – REFDT1. For time points on or after REFDT1, the Study Day = time point – REFDT1 + 1. Thus, the Study Day is a negative value when the time point of interest is prior to REFDT1 and the Study Day is a positive value when the time point of interest is on or after REFDT1. There is no Study Day 0. The Study Day will be labeled as Rx Day on the data listings. Study Days during Extension Period will be calculated based on the Extension Period start reference date (REFDT2) with the same rule as in 26-week randomized treatment period. For OMT subjects who enter the Extension Period, the study day of Pre in Extension Period will be calculated based on REFDT2.

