10.2 Analysis of Adverse Events

All adverse events will be coded using the most current version of the Medical Dictionary for Regulatory Activities (MedDRA). Adverse events will be summarized by primary MedDRA system organ class (SOC) and preferred term (PT). Subjects reporting more than one adverse event for a given PT will be counted only once for that term. Subjects reporting more than one adverse event within an SOC will be counted only once for the SOC total. Subjects reporting more than one adverse event will be counted only once in the overall adverse event total. For summaries by SOC and PT, the SOCs will be presented in alphabetical order and the PTs will be presented in alphabetical order within each SOC.

A treatment-emergent adverse event (TEAE) during the 26-week randomized treatment period is defined as:

- For subjects in OMT group who don't continue into Extension Period: any adverse event that begins or worsens in severity the day after randomization and within 30 days following the last visit.
- For subjects in OMT group and continue into Extension Period: any adverse event that begins or worsens in severity the day after randomization and within 30 days following the last visit during 26-week randomized treatment period or before the insertion of NJ/PEG-J (whichever is earlier).
- For LCIG treatment subjects who have all study tubes removed after their last study drug infusion, this includes all adverse events with onset on or after the date of the initial tube placement procedure and no more than 30 days following the last study tube removal, or no more than 30 days following the last LCIG infusion if there is no final device removal during the 26-week randomized treatment period.

A TEAE during Extension Period for OMT subjects will be defined as any adverse event that begins or worsens in severity after the NJ or PEG-J placement through 30 days after last LCIG infusion or final device removal (whichever is later).

A TEAE during the continuing LCIG treatment period will be defined as any adverse event in LCIG group that begins or worsens in severity after Week 26 visit through 30 days after last LCIG infusion or final device removal (whichever is later).

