12.0 Summary of Changes

This SAP contains no change in analysis from the latest version of the protocol (Protocol Amendment 4).

The changes in this SAP from SAP V1.0 is: Per protocol amendments, subjects from South Korean/United States who complete the 26-week clinical study will have the option to enter an extension of the study. This SAP added the description for Extension Period analyses.

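### SAP 10.2 does not assign events after Week 26 in continuing LCIG subjects to one period, so they can enter the randomized-period comparison with OMT

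*SAP*

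**What the plan says.** SAP Section 10.2 has one bullet for the LCIG arm in the randomized period. Its lead-in limits it: "For LCIG treatment subjects who have all study tubes removed after their last study drug infusion". Its last clause then covers a different case and sets the end of the window at "no more than 30 days following the last LCIG infusion if there is no final device removal" within the 26 weeks.

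For continuing LCIG treatment, the same section counts an event that "begins or worsens in severity after Week 26 visit through 30 days after last LCIG infusion or final device removal".

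SAP Section 6.2 says when the randomized period closes for an LCIG subject. It names the date on which the final tube comes out, "or the date of the last LCIG infusion if there is no device removal in the 26-week randomized period will be considered as end". For a subject who keeps the tube, the period therefore closes with the last infusion in the 26 weeks.

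OMT subjects have two bullets. Those who do not enter the Extension are counted to 30 days after the last visit. Those who enter it are counted to 30 days after the last randomized-period visit or to tube insertion, whichever comes first. LCIG subjects have no such cut-off.

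Protocol Section 8.1.4.2 sets the LCIG window to run "through Week 26 Visit for those subjects continuing to LCIG commercial treatment", and to 30 days after final device removal for the others. SAP Section 12.0 states: "This SAP contains no change in analysis from the latest version of the protocol", and names Amendment 4 as that version.

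**The concern.** An LCIG subject who continues after Week 26 normally keeps the tube, so the last clause of the LCIG bullet appears to describe exactly that subject. It adds 30 days to a period after which treatment carries on. The continuing-period window is already open during those days, and nothing in the SAP says which period an event belongs to.

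The stake is the between-arm safety comparison. SAP Section 10.2.2 tests randomized-period TEAE percentages between LCIG and OMT with Fisher's exact test. An LCIG subject with no event up to Week 26 and one on Day 195 would count in that comparison, although the event arose under continuing treatment. The same definition feeds the 26-week severity, relationship, special-interest and subgroup tables. The event can also appear in the Extension/Transition summaries, which are planned for the overview and for any, serious and discontinuation-related TEAEs.

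**Working it through.** **Inputs**
- Nominal Week 26: Day 182 (SAP Tables 1 and 6).
- Visit window from Week 6 on: ±7 days (Protocol 5.3.1).
- Randomized-period tail: 30 days after the last infusion (SAP 10.2), with the last infusion taken as the last one in the 26 weeks (SAP 6.2).
- Start of the continuing window: the day after the Week 26 visit (SAP 10.2).

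**The plan's own figure.** 26 × 7 = 182, which matches the last day of the final interval in SAP Table 6.

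**Overlap, LCIG subject who keeps the tube.** Overlap = (last infusion day + 30) − (visit day + 1) + 1.

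| Visit day | Last randomized-period infusion | Randomized window ends | Continuing window starts | Overlap |
|---|---|---|---|---|
| 182 | 182 | 212 | 183 | 30 days |
| 182 | 181 | 211 | 183 | 29 days |
| 175 | 175 | 205 | 176 | 30 days |
| 175 | 174 | 204 | 176 | 29 days |
| 189 | 189 | 219 | 190 | 30 days |
| 189 | 188 | 218 | 190 | 29 days |

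Relative to the nominal period, 30/182 = 16.5% and 29/182 = 15.9%.

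**Same subject under the protocol's end point.** The randomized window is Days 1 to 182 and the continuing window starts on Day 183: overlap 0.

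**OMT subject who enters the Extension.** The randomized window ends at the earlier of Day 182 + 30 and the day before tube insertion.
- Tube 5 days after the visit (Day 187): the window ends on Day 186, overlap 0.
- Tube 45 days after the visit (Day 227): the window ends on Day 212, overlap 0.

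**Alternative readings of the LCIG bullet**
- Lead-in read strictly (all tubes removed): a subject who keeps the tube has no randomized-period TEAE definition.
- Last infusion read as the last in the whole study: the overlap becomes the entire continuing period. SAP 6.2 supports the narrower reading, so 29 to 30 days is the smaller overlap.

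**Consistency with the rest of the SAP.** The epochs in SAP 6.2 do not overlap: the LCIG extension epoch starts the day after the last randomized-period infusion. Table 6 stops at Day 182, so an event in the tail, in either arm, has no week interval.

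**What happens if only the LCIG window is shortened.** Continuing LCIG subjects would have 182 days. OMT subjects who do not enter the Extension would keep 182 + 30 = 212 days. The difference of 30 days would favour LCIG.

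**The case against.** The strongest reply is that the LCIG bullet, by its lead-in, was never meant for subjects who keep their tube. That ambiguity is real. It does not rescue the text: on that reading continuing LCIG subjects have no randomized-period rule, which calls for the same edit.

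The second reply is that the present text does little harm to balance between arms. The Extension is open only in the United States and South Korea (SAP 4.2). Elsewhere, OMT completers and continuing LCIG subjects are both followed to about Day 212. This stands, and it is why adopting the protocol's end point for LCIG alone would be the wrong remedy. Under the current text the unequal follow-up concerns OMT Extension entrants whose tube is placed within 30 days.

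Third, a reader might infer that every event in the 30 days is double counted. The documents do not support that. Each subject counts once per preferred term, system organ class and overall within a table, and no total across periods is planned. The duplication is across tables. A tail event in a term that the subject has already reported changes no incidence count for that term.

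Fourth, a reader might take the protocol conflict to cover all continuing subjects. Protocol 8.1.4.2 speaks only of those going on to commercial LCIG. The country amendments that added the Extension are not among the documents and may define TEAEs differently for those subjects.

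**Conclusion.** The point holds in this form: SAP 10.2 does not place post-Week-26 events of continuing LCIG subjects in one period. If the last clause governs, the windows overlap by 29 to 30 days. If the lead-in governs, the randomized-period definition is missing. On both readings the SAP differs from Protocol 8.1.4.2 for subjects moving to commercial LCIG, and SAP Section 12 does not say so. The internal overlap does not depend on any protocol text.

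The size is a window length of about 16% of 182 days per continuing LCIG subject. It is tempting to read this as a 16% inflation of the LCIG event rate. The documents give neither the number of subjects who continue nor the event rate in that month, so no effect on a percentage or P value can be derived. The efficacy endpoints are untouched.

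The calculation assumes that the Week 26 visit falls within its ±7 days and that the last counted infusion is on the visit day or the day before. The text needs correcting before the safety tables are programmed.

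**What to change.** 1. Add an LCIG bullet to SAP 10.2 for subjects who continue LCIG after Week 26, by commercial transition or Extension. End their randomized-period window at the Week 26 visit and start the continuing period the next day.
2. For the between-arm TEAE tables and Fisher tests, use the same cut-off in both arms: the Week 26 visit for all completers, including OMT subjects who do and who do not enter the Extension.
3. Report OMT events in the 30 days after the last visit in a separate table, keeping the existing cap at 30 days or tube insertion.
4. Keep the 30-day tail after last infusion or device removal for LCIG subjects who stop, shown apart from the on-treatment comparison.
5. List these changes in SAP Section 12, since they also alter the Protocol 8.1.4.2 windows for OMT subjects and for LCIG subjects who stop, and check them against the country amendments.

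The cost is wording and programming. The drawback is that a few post-Week-26 OMT events, and the tail events of LCIG subjects who stop, move from the comparison to separate tables. No event is lost, and each is assigned to one period.

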10.2.1 Adverse Event Overview

The number and percentage of subjects experiencing one or more adverse events in the following adverse event categories during the 26-week Treatment Period and during the Extension/Transition Period will be summarized.

- Any TEAE
- Any TEAE that was rated by the investigator as having a reasonable possibility of relationship to levodopa-carbidopa intestinal gel
- Any severe TEAE
- Any serious TEAE
- Any TEAE that led to discontinuation of study drug
- Any treatment emergent GI event (as defined in Section 10.2.3)
- Any TEAE other than a GI event (as defined in Section 10.2.3)
- A fatal TEAE
- All deaths

Serious adverse events with onset during the Screening Period for all subjects screened, adverse events and serious adverse events with onset after day of randomization and before day of initial device placement for the LCIG group, as well as adverse events during the transition period for LCIG subjects continuing LCIG commercial treatment will also be summarized.

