5.5.3 Method of Assigning Subjects to Treatment Groups

Before the site is initiated, contact information and user guidelines for the IRT system will be provided to each site. Upon receipt of study drug, the site will acknowledge receipt in the IRT system.

At Screening during Visit 1, each subject will be assigned a unique 5-digit number by the IRT system. Following Visit 3, the site will contact the IRT to randomize the subject to OMT or LCIG. Subjects randomized to OMT will continue on their current anti-PD medication regimen for the duration of the study. For subjects randomized to LCIG, the site will obtain the study drug kit numbers to dispense at the designated Visits. Study drug must not be dispensed without contacting the IRT. Study drug may only be dispensed to subjects randomized to LCIG in the study through the IRT.

This is an open-label study and all eligible subjects will receive OMT or LCIG.

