6.1.3 Relationship to Study Drug

For the assessment of drug event relationship, LCIG should be considered a therapeutic system consisting of drug, devices and placement procedure. Causality assessments are always made over the system as a whole.

For the assessment of drug event relationship, those randomized to OMT should evaluate relatedness to any of the subject's anti-PD medication.

The Investigator will use the following definitions to assess the relationship of the adverse event to the use of study drug:

Reasonable Possibility	After consideration of factors including timing of the event, biologic plausibility, clinical judgment, and potential alternative causes, there is sufficient evidence (information) to suggest a causal relationship.
No Reasonable Possibility	After consideration of factors including timing of the event, biologic plausibility, clinical judgment, and potential alternative causes, there is insufficient evidence (information) to suggest a causal relationship.

For causality assessments, events assessed as having a reasonable possibility of being related to the study drug will be considered "associated." Events assessed as having no reasonable possibility of being related to study drug will be considered "not associated." In addition, if the Investigator has not reported causality or deemed it not assessable, AbbVie will consider the event associated.

[figure not shown]
If an Investigator's opinion of no reasonable possibility of being related to study drug is given, an Other cause of event must be provided by the Investigator for the serious adverse event.

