10.2.2 Adverse Event Incidence

The number and percentage of subjects experiencing one or more adverse events in the following adverse event categories during the 26-week Treatment Period will be summarized for each treatment group and for overall subjects by primary SOC and PT.

- Any TEAE
- Any serious TEAE
- Any TEAE that led to discontinuation of study drug

The percentage of subjects in the LCIG group and in the OMT group will be compared using Fisher's exact test. Only P values ≤ 0.100 when rounded to three digits will be presented.

The number and percentage of subjects experiencing one or more adverse events in the following adverse event categories during the Extension/Transition Period will be summarized for OMT/LCIG subjects who enter the Extension/Transition Period by primary SOC and PT.

- Any TEAE
- Any serious TEAE
- Any TEAE that led to discontinuation of study drug

The number and percentage of subjects experiencing one or more TEAEs during the 26-week Treatment Period will also be summarized for each treatment group and for overall subjects by maximum severity category (mild, moderate, severe, or unknown) and primary SOC and PT. Subjects reporting more than one TEAE for a given PT will be counted only once for that term in the most severe category reported. If a subject has an adverse event with unknown severity, then the subject will be counted in the severity category of "unknown," even if the subject has another occurrence of the same event with a severity present. The only exception is if the subject has another occurrence of the same

adverse event with the most extreme severity – "Severe." In this case, the subject will be counted under the "Severe" category.

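### The related-event row of the SAP safety overview counts only LCIG-related events, so the 26-week OMT count is zero by definition; the discontinuation row is ambiguous for OMT

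*SAP*

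**What the plan says.** **Relatedness.** SAP 10.2.1 lists the overview categories. One is "Any TEAE that was rated by the investigator as having a reasonable possibility of relationship to levodopa-carbidopa intestinal gel". The overview is to be prepared for events "during the 26-week Treatment Period and during the Extension/Transition Period will be summarized", with no different wording for the two periods or the two arms. Protocol 6.1.3 sets the rating rule for the comparator: "For the assessment of drug event relationship, those randomized to OMT should evaluate relatedness to any of the subject's anti-PD medication". Protocol 8.1.4.2 asks for "TEAEs by maximum relationship to study drug". SAP 10.2.2 provides that table for each treatment group, using the investigator's rating and naming no drug.

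**Discontinuation.** Protocol 8.1.4.2 asks for "TEAEs leading to premature discontinuation of treatment". SAP 10.2.1, 10.2.2 and 10.2.5 use a different category: "Any TEAE that led to discontinuation of study drug". SAP 10.2.2 compares this category between arms with Fisher's exact test and presents only P values of 0.100 or less.

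**Consistency statement.** SAP 12.0 says that the analysis is unchanged from Protocol Amendment 4.

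**The concern.** Tolerability of LCIG relative to OMT is a secondary objective (Protocol 4.0). Related events and events leading to discontinuation are two of the first rows a reader looks at for it.

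In the first row, an OMT event that the investigator correctly rates as related to, say, a dopamine agonist does not meet the SAP category. A real LCIG count would stand beside an OMT zero produced by the wording. The same report would also carry a different OMT figure in the SAP 10.2.2 relationship table.

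In the second row, an OMT subject who leaves the study because of an adverse event may or may not count, depending on what study drug means for that arm. If such subjects are left out, a tested comparison is biased against LCIG.

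**Working it through.** The documents state no figure to reproduce here. The check compares sections and then illustrates the possible size.

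**1. Related-event row, 26-week period.**
- Category (SAP 10.2.1): a reasonable possibility of relationship to LCIG.
- Rating collected for OMT (Protocol 6.1.3): relationship to any of the subject's anti-PD medication.
- LCIG exposure of OMT subjects in the randomized period: none (Protocol 5.5.3: "Study drug may only be dispensed to subjects randomized to LCIG in the study through the IRT").

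No event arising on OMT can meet the category, so the literal count is 0. One marginal route exists. An OMT subject outside the extension could start commercial LCIG after the last visit (Protocol 5.1.3) and have an event within the 30-day tail of the event window (SAP 10.2). That would not be randomized treatment.

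**2. Related-event row, Extension/Transition Period.** Former OMT subjects in the United States and South Korea receive LCIG in the extension (SAP 4.2). The LCIG wording is meaningful there.

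**3. What study drug means.**

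| LCIG only | Both arms |
|---|---|
| Protocol 1.2, screening text: the term is glossed as LCIG | SAP 7.1: study drug discontinuations summarised for both groups |
| Protocol 5.5.3: dispensed only to the LCIG arm | SAP 6.7: the study drug exposure dataset holds OMT medications |
| SAP 8.1: drug exposure for LCIG, study participation for OMT | Protocol 8.1.4.1: heading covers OMT and LCIG exposure |

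The term is inconsistent. A zero for OMT in the discontinuation row is possible but does not follow from the text.

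**4. Size, under the LCIG-only reading.** Inputs: 44 per arm (Protocol 1.2) and assumed event counts, because the documents give none. For k versus 0 with equal arms, the two-sided Fisher P value is 2 × C(44,k) / C(88,k).
- k = 5: 2 × 1,086,008 / 39,175,752 = 0.055
- k = 6: 2 × 7,059,052 / 541,931,236 = 0.026

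For 6 versus 2, the eight events fall 0, 1 or 2 to one arm with probabilities 0.00276 + 0.02623 + 0.10389 = 0.1329. Doubling gives P = 0.27. Likewise, 8 versus 0 gives P = 0.006 and 8 versus 3 gives P = 0.20. Since SAP 10.2.2 prints only P values up to 0.100, the versus-0 results would be shown and the others would not.

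The safety dataset drops LCIG subjects with no device placed. If that left 40 against 44, then 4 versus 0 would already give P = 0.047.

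**5. False-positive rate if a row with OMT fixed at zero were tested.** At 44 per arm, rejection at 0.05 needs at least 6 LCIG subjects, so the rate is Pr[Bin(44, p) ≥ 6]. Assume the same true rate p in both arms:

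| p | OMT fixed at 0 | Arm-neutral count |
|---|---|---|
| 5% | 2.2% | 0.5% |
| 10% | 27.4% | 1.9% |
| 15% | 66.4% | 2.5% |
| 20% | 89.8% | 2.5% |
| 30% | 99.7% | 2.8% |

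For the related-event row, such a test would come only from the general rule for binary safety variables in SAP 10.1. SAP 10.2.1 names no test, and the categories tested in SAP 10.2.2 do not include related events.

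**The case against.** The strongest reply is that this is loose terminology with little effect.

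- **Relatedness is reported properly elsewhere.** SAP 10.2.2 tabulates maximum relationship by arm from the investigator's rating, which for OMT means the Protocol 6.1.3 rating. This stands. A reader might infer that the SAP redefines relatedness throughout; it does so in one overview row only. The summary the protocol asked for is retained, so this row alone does not show the no-change statement in SAP 12.0 to be wrong.
- **A programmer would use the single relationship field for both arms.** Possibly, but then the row label is wrong for OMT. Either the count or the label needs correcting.
- **Discontinuation of study drug can be read to cover OMT.** This stands. A reader might infer that both rows are zero for OMT by construction. SAP 7.1, SAP 6.7 and Protocol 8.1.4.1 do not support that for the discontinuation row.
- **OMT subjects do receive LCIG.** True in the extension for some countries, so the point is confined to the 26-week period.
- **Discontinuations by arm are summarised in any case.** SAP 7.1 gives them by reason, and Protocol 8.1.2 plans Fisher tests of them. That softens the consequence but does not say which events belong in the SAP 10.2.2 table or the SAP 10.2.5 listing.

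**Conclusion.** The point holds for the related-event row. In the 26-week period, the category as written excludes every event arising on OMT, departs from the rating rule in Protocol 6.1.3, and disagrees with the SAP's own relationship table.

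For the discontinuation row the finding is ambiguity: two programmers could follow the SAP and produce different OMT counts for a tested comparison.

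The Fisher contrasts (6 versus 0, P = 0.026, against 6 versus 2, P = 0.27) rest on assumed counts, 44 per arm and the LCIG-only reading. They show what that reading could do and do not predict the result. Any bias would run against LCIG. Primary and key secondary efficacy conclusions are unaffected. The correction should be made because it is cheap and concerns a stated secondary objective.

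**What to change.** 1. **SAP 10.2.1, 26-week period.** Replace the LCIG-specific relatedness wording with: *relationship to study treatment (LCIG system for the LCIG arm; any anti-PD medication for the OMT arm, per Protocol 6.1.3)*. Keep the LCIG wording for the Extension/Transition Period.
2. **SAP 10.2.1, 10.2.2 and 10.2.5.** Replace the study-drug wording with: *premature discontinuation of randomized treatment or of the study*. Identify these events in both arms from the event-level adverse event record, where Protocol 6.1 already requires any action taken. Cross-check against all recorded discontinuation reasons. The primary reason alone is not enough: Protocol 8.1.2 allows several reasons per subject, and a disposition reason does not identify the event needed for a table by system organ class and preferred term.

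The cost is SAP wording plus a programmed cross-check. Relatedness ratings, action taken and discontinuation reasons are already collected in both arms.
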